Statistical Methodology	This is a stratified phase II study of escalating fractions of stereotactic body radiotherapy (SBRT) combined with immunotherapy for previously untreated or previously treated metastatic melanoma patients. Phase I was stratified by site: bone or lung vs. liver or s.c. Six patients were enrolled per dose cohort. Phase II is stratified by site: bone or lung vs. liver or s.c. In phase II, 20 patients will be treated at the MTD in each stratum. Descriptive statistics will be generated for both phases of the study.

CONFIDENTIAL

This material is the property of the sponsor. Do not disclose or use except as authorized in writing by the study sponsor

Printed on 1/31/2017

1 Introduction

This document is a protocol for a human research study. This study is to be conducted according to US and international standards of Good Clinical Practice (FDA Title 21 part 312 and International Conference on Harmonization guidelines), applicable government regulations and Institutional research policies and procedures.

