8.1 Design

This is a stratified Phase II study of escalating fractions of stereotactic body *radiotherapy* (SBRT) combined with immunotherapy for previously untreated or previously treated metastatic melanoma patients. Patients will undergo a short course of high dose SBRT to a single index lesion that is suitable for SBRT. These fractions will be administered several days apart. Radiotherapy will be immediately followed by ipilimumab, at the FDA-approved dose and schedule.

Stratified Phase II study: With safety data from an identical University of Pennsylvania study, SBRT fractions of two and three fractions has been shown to be safe. At UW/SCCA the Phase II study begins with Dose Level 1. If three fractions of SBRT are found to not be safe, the dose level will be reduced to Dose level -1 for the phase II portion of that stratum.

Stratification by Site of Index Lesion						
Dose Level	Stratum 1: bone or lung			Stratum 2: liver or subcutaneous		
	Dose per fraction	Fractions	# Patients	Dose per fraction	Fractions	# Patients
-1	8 Gy	2	6	6 Gy	2	6
1	8 Gy	3	6	6 Gy	3	6

The MTD has been defined by the Phase I trial at the University of Pennsylvania as 3 fractions of SBRT. The Phase II study can commence at UW/SCCA at dose level 1 (above). Patients will be treated at the MTD defined for their index lesion site. In Phase II, patients will be stratified by disease site: Stratum 1: phase 1 bone or lung and Stratum 2: phase 1 liver or subcutaneous. Stratum-specific response rates will be calculated. Enrollment will proceed independently for the

CONFIDENTIAL

This material is the property of the study sponsor. Do not disclose or use except as authorized in writing by the study sponsor

Printed on 1/31/2017

two strata. Forty total patients will be enrolled in this phase. Thus a maximum of 40 patients will be entered at the MTD. Twenty patients will be enrolled in each stratum

8.2 Objectives:

Phase II study: The primary objectives are to determine for each stratum, immune-related clinical response rate, immune-related progression-free survival rate at 6 months (irPFS6), and overall survival rate at 12 months (OS12). The secondary objectives are to gather additional data on acute and late toxicity and immune pharmacodynamic changes.

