8.5 Plans for Data Analysis

Toxicity: Any patient who receives any amount of radiation or study medication will be analyzed for toxicity. All dose-limiting toxicities and late toxicities will be graded and tabled by lesion site

CONFIDENTIAL

This material is the property of the study sponsor. Do not disclose or use except as authorized in writing by the study sponsor

Printed on 1/31/2017

stratum and SBRT fraction dose level. Toxicity attribution to either SBRT or ipilimumab will be described if possible.

Response: Clinical response at a non-index lesion will be scored using the immune-related response criteria (irRC) referred to as irRECIST 1.1 and discussed by others.(25,26) The index lesion will not be included in measuring response. The number of immune-related responses will be tabled by stratum and SBRT fraction dose level. **At the MTD**, the immune-related response rate and 95% exact CI will be estimated separately for previously untreated and previously treated metastatic patients and will inform our decision-making. The table below displays 95% exact CIs for selected numbers of responses.

95% Exact Confidence Interval for Event Rate based on 14 patients in each stratum at the Maximum Tolerated SBRT Fraction					
No. of Events	%	95% exact CI	No. of Events	%	95% exact CI
2	14.3	1.8 – 42.8	10	71.4	41.9 – 91.6
4	28.6	8.4 – 58.1	12	85.7	57.2 – 98.2
6	42.9	17.7 – 71.1	14	100.0	80.7*
8	57.1	28.9 – 82.3	* lower bound of 95% 1-sided CI		

Immune-related progression-free and overall survival will be estimated by the Kaplan-Meier method separately for previously untreated and previously treated metastatic patients who were treated at the MTD. The estimated 6 month irPFS and 12 month OS rates and 95% CIs will inform our decision-making, as they are considered by many to be better measures of clinical benefit. Interestingly, PFS6 and OS12 rates were approximately 25% and 45%, respectively, in 137 previously treated metastatic melanoma patients treated with ipilimumab alone.(3) Evaluation using historical benchmarks has been proposed by Korn et. al. for Phase II decision-making in metastatic melanoma (27).

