8.6 Sample Size/Power

If the Phase II study investigates both SBRT fraction dose levels for both strata, then a total of 40 patients will be enrolled on the study. There will be 40 patients enrolled at the Phase II dose. An objective response rate of 10.9% (by modified WHO criteria) was observed by Hodi et. al. in 137 previously treated metastatic melanoma patients treated with ipilimumab alone.(3) We anticipate that the combination of SBRT and ipilimumab will result greater efficacy for each stratum. If the true immune-related response rate is 20%, then the probability of observing no responses in 14 patients in either stratum, is <0.05.

With regard to statistical power, our preliminary clinical data on 16 patients treated on the single-infusion CD40 mAb trial indicate the mean difference \pm SD_{diff} between post- and pre-treatment percentages of CD19+ B cells expressing CD86 were: 17.1% \pm 11.1%, with effect size of 1.5 SD_{diff} units. By pooling over strata at the MTD, with a total of 28 patients enrolled, there is >80% power to detect a more modest effect size of $\frac{3}{4}$ SD_{diff} units, based on a paired t-test at 2-sided alpha level of 0.005 after adjusting for testing of multiple APC measures. Moreover, at the end of our current Phase I study of anti-CTLA-4 antibody (tremelimumab) and anti-CD40 antibody (CP-870,893) (UPCC 05609), we will evaluate pre/post differences in percentages of CD19+ B cells expressing CD86 and other relevant immune outcomes and we will update the power calculation for those effect sizes.

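### The plan puts 20 patients per stratum (40 in total) at the MTD, but its confidence intervals, zero-response probability and power are computed for 14 and 28

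*Combined protocol and SAP*

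**What the plan says.** Two sizes are given for the same group, the patients treated at the MTD.

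- **20 per stratum, 40 in total.** Study Summary, Statistical Methodology: "In phase II, 20 patients will be treated at the MTD in each stratum". Section 8.1: "Thus a maximum of 40 patients will be entered at the MTD" and "Twenty patients will be enrolled in each stratum". Section 8.6: "There will be 40 patients enrolled at the Phase II dose".
- **14 per stratum, 28 in total.** The table in 8.5 is headed "95% Exact Confidence Interval for Event Rate based on 14 patients in each stratum at the Maximum Tolerated SBRT Fraction". Section 8.6 says that at a true response rate of 20%, "then the probability of observing no responses in 14 patients in either stratum, is <0.05". Its power statement for the paired t-test begins "By pooling over strata at the MTD, with a total of 28 patients enrolled".

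Section 8.6 also opens with a third use of 40: "If the Phase II study investigates both SBRT fraction dose levels for both strata, then a total of 40 patients will be enrolled". Section 3.1 caps the whole protocol at 40 patients.

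**The concern.** The plan is mainly descriptive and has no hypothesis test on response. The interval table in 8.5 is therefore the only display of precision for the response rate, which 8.2 makes a primary objective for each stratum. If that table does not describe the planned group, the reader cannot tell what precision, or what immunologic power, the trial is designed to have, or whether a stratum is complete at 14 or at 20 patients at the MTD.

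The first two sentences of 8.6 add to the difficulty. The first makes 40 the study total when both dose levels are used in both strata; the second places 40 at a single dose. Under the cap of 40 in 3.1, each patient treated at the other level takes the MTD group below 40, so both sentences cannot hold when the condition in the first is met.

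**Working it through.** **Inputs.** MTD group of 14 per stratum and 28 pooled (8.5, 8.6), or 20 and 40 (Study Summary, 8.1, 8.6). True response rate 20% (8.6). Effect of 0.75 SD of the paired difference, two-sided alpha 0.005, paired t-test (8.6).

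**1. The plan's own figures.**

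- Clopper-Pearson 95% limits at n = 14 are 1.8–42.8 (2 events), 8.4–58.1 (4), 17.7–71.1 (6), 28.9–82.3 (8), 41.9–91.6 (10) and 57.2–98.2 (12). All six match the 8.5 table. The one-sided lower bound for 14/14 is 0.05^(1/14) = 0.807, also as printed.
- Probability of no responses in one stratum: 0.8^14 = 0.044, below 0.05 as stated.
- Power from the noncentral t distribution, with n − 1 degrees of freedom and noncentrality 0.75 × √n: 0.808 at n = 28, above 80% as stated. At n = 27 it is 0.786, so 28 only just clears 80%.

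The printed figures were therefore computed for 14 and 28, and correctly.

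**2. The same quantities at 20 and 40.**

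| Quantity | 14 / 28 | 20 / 40 |
|---|---|---|
| Exact 95% CI at 50% observed, per stratum | 7/14: 23.0–77.0 (width 53.9) | 10/20: 27.2–72.8 (width 45.6) |
| One-sided lower bound if all respond | 80.7% | 0.05^(1/20) = 86.1% |
| P(no responses, true rate 20%), per stratum | 0.044 | 0.8^20 = 0.012 |
| Power at 0.75 SD, pooled | 0.808 | 0.955 |
| Effect detectable with 80% power, pooled | 0.74 SD | 0.61 SD |

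**3. The wording of the zero-response sentence.** The stated bound holds per stratum. If the sentence is read as no responses in at least one of the two strata, the probability is 1 − (1 − 0.044)² = 0.086 at 14 and 1 − (1 − 0.0115)² = 0.023 at 20. The bound would then fail at 14.

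**4. Can the two sizes be bridged?**

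- *Evaluability.* For response, 8.3 keeps unevaluable patients in the denominator. The 28 in 8.6 are described as enrolled. No dropout allowance that would turn 20 into 14 is stated.
- *Subtraction.* The dose table in 8.1 lists six patients per stratum at each dose level. Six per stratum at the other level would leave 20 − 6 = 14 per stratum and 40 − 2 × 6 = 28 in total. This is the best source the text offers for 14 and 28, but the plan never states it. If it was intended, the statements of 20 and 40 at the MTD are wrong.

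**The case against.** The strongest reply is that the numbers can be reconciled. In 8.1 the 40 at the MTD is a maximum, and the 20 per stratum is not tied to a dose in that sentence. The opening of 8.6 is conditional, so 40 could be the study total, with all 40 at one dose only if nobody is de-escalated. This has some force for 8.1. However, 8.1 also says that patients will be treated at the MTD, and it derives the maximum directly from the phase total. The Study Summary and the second sentence of 8.6 carry no such qualification. No reading makes those two agree with 28 enrolled at the MTD.

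A second reply is that the subtraction is conjecture and fits the current rules poorly. Enrolment starts at Dose level 1, with the MTD taken from the earlier trial, and the strata enrol independently. A group of exactly 14 and 14 would need both strata to switch after six patients each. This stands, and the subtraction should be treated as a possible origin only.

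Three limits also stand. First, if all 40 patients are treated at one level, the printed figures are conservative. Second, the power of 0.955 needs paired samples from all 40, while 7.1.2 makes immune assessment depend on the cells or serum available; this power also serves a secondary objective. Third, 8.5 estimates the response rate separately for previously untreated and previously treated patients and gives no size for those groups. An n = 20 table would thus show precision for the stratum-specific rates promised in 8.1, but not for that analysis.

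**Conclusion.** The concern holds. The plan gives two sizes for the MTD group, differing by 6 per stratum and 12 in total, and nothing in the text bridges them. Section 8.6 is also inconsistent on what 40 covers.

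The consequence is confined to stated precision and power; no decision threshold in the plan depends on this number. If all 40 patients are treated at one dose level, both inequalities in 8.6 remain true, with the zero-response statement read per stratum and paired samples available for the power, and the intervals are narrower than printed. If 40 covers both levels, the printed figures may stand, but the Study Summary, 8.1 and 8.6 overstate the MTD group. Confidence in the mismatch is high; where 14 and 28 came from is inference. The correction should be made, but it does not threaten the design.

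**What to change.** Decide the intended MTD sample size, state in 8.6 whether 40 is the total across dose levels or the number at the Phase II dose, and make the Study Summary, 8.1, 8.5 and 8.6 agree.

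- **If 20 and 40:** replace the 8.5 table with exact intervals for n = 20: 2/20 1.2–31.7; 4/20 5.7–43.7; 6/20 11.9–54.3; 10/20 27.2–72.8; 14/20 45.7–88.1; 18/20 68.3–98.8; 20/20 one-sided lower bound 86.1. In 8.6, give the zero-response probability as 0.012 per stratum. Give the power as 0.95 for 0.75 SD, or 80% for 0.61 SD, conditional on paired samples from all 40. Reword the first sentence of 8.6.
- **If 14 and 28:** keep the table and both 8.6 figures, adding that the zero-response probability is per stratum. State how 14 and 28 arise; if it is six per stratum at the other level, say so. Correct the statements of 20 per stratum and 40 at the MTD or Phase II dose in the Study Summary and 8.6, and make clear in 8.1 that 20 and 40 count both dose levels.
- **If the size depends on whether de-escalation under 8.4.1 occurs:** say so, and label each set of figures with its case.

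The cost is one decision and text edits, plus one recomputed table in the first case. The design does not change.

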8.7 Study Duration

With an estimated accrual of 15 patients per year, it is anticipated that accrual will continue for 3.0 to 3.5 years, allowing for observation time within and between dose levels.

9 Safety Assessment and Adverse Event Reporting

It is the responsibility of the Principal Investigator to oversee the safety of the study at his/her site. This safety monitoring will include careful assessment and appropriate reporting of adverse events as noted above, as well as the construction and implementation of a site data and safety-monitoring plan (see section 10). Medical monitoring will include a regular assessment of the number and type of serious adverse events.

9.1 Definitions

Unanticipated Problems Involving Risk to Subjects or Others

Any incident, experience, or outcome that meets all of the following criteria:

- Unexpected in nature, severity, or frequency (i.e. not described in study-related documents such as the IRB-approved protocol or consent form, the investigators brochure, etc)
- Related or possibly related to participation in the research (i.e. possibly related means there is a reasonable possibility that the incident experience, or outcome may have been caused by the procedures involved in the research)
- Suggests that the research places subjects or others at greater risk of harm (including physical, psychological, economic, or social harm).

Adverse Event

CONFIDENTIAL

This material is the property of the study sponsor. Do not disclose or use except as authorized in writing by the study sponsor

Printed on 1/31/2017

An **adverse event** (AE) is any symptom, sign, illness or experience that develops or worsens in severity during the course of the study. Intercurrent illnesses or injuries should be regarded as adverse events. Abnormal results of diagnostic procedures are considered to be adverse events if the abnormality:

- results in study withdrawal
- is associated with a serious adverse event
- is associated with clinical signs or symptoms
- leads to additional treatment or to further diagnostic tests
- is considered by the investigator to be of clinical significance

Serious Adverse Event

Adverse events are classified as serious or non-serious. A **serious adverse event** is any AE that is:

- fatal
- life-threatening
- requires or prolongs hospital stay
- results in persistent or significant disability or incapacity
- a congenital anomaly or birth defect
- an important medical event

Important medical events are those that may not be immediately life threatening, but are clearly of major clinical significance. They may jeopardize the subject, and may require intervention to prevent one of the other serious outcomes noted above. For example, drug overdose or abuse, a seizure that did not result in in-patient hospitalization, or intensive treatment of bronchospasm in an emergency department would typically be considered serious.

All adverse events that do not meet any of the criteria for serious should be regarded as **non-serious adverse events**.

9.2 Adverse Events

Assessment of adverse events will include type, incidence, severity (graded by the National Cancer Institute [NCI] Common Terminology Criteria for Adverse Events [CTCAE], Version 4.03), timing, seriousness, and relatedness; and laboratory abnormalities. Patients who receive 1 or more study treatments will be evaluable for toxicity.

9.2.1 Adverse Event Reporting

In the event of an adverse event the first concern will be for the safety of the subject. The study period during which adverse events must be reported is normally defined as the period from the initiation of any study procedures to the end of the study treatment follow-up. For this study, the study treatment follow-up is defined as 30 days following the last administration of study treatment. Thereafter, only non-hematological related AEs of Grade 3 and can reasonably be attributed to the study treatment will be reported.

Preexisting Condition

A preexisting condition is one that is present at the start of the study. A preexisting condition should be recorded as an adverse event if the frequency, intensity, or the character of the condition worsens during the study period.

General Physical Examination Findings

CONFIDENTIAL

This material is the property of the study sponsor. Do not disclose or use except as authorized in writing by the study sponsor

Printed on 1/31/2017

At screening, any clinically significant abnormality should be recorded as a preexisting condition. At the end of the study, any new clinically significant findings/abnormalities that meet the definition of an adverse event must also be recorded and documented as an adverse event.

Post-study Adverse Event

All unresolved adverse events should be followed by the investigator until the events are resolved, the subject is lost to follow-up, or the adverse event is otherwise explained. At the last scheduled visit, the investigator should instruct each subject to report any subsequent event(s) that the subject, or the subject's personal physician, believes might reasonably be related to participation in this study. The investigator should notify the study sponsor of any death or adverse event occurring at any time after a subject has discontinued or terminated study participation that may reasonably be related to this study. The sponsor should also be notified if the investigator should become aware of the development of cancer or of a congenital anomaly in a subsequently conceived offspring of a subject that has participated in this study.

Abnormal Laboratory Values

A clinical laboratory abnormality should be documented as an adverse event if any one of the following conditions is met:

- The laboratory abnormality is not otherwise refuted by a repeat test to confirm the abnormality
- The abnormality suggests a disease and/or organ toxicity
- The abnormality is of a degree that requires active management; e.g. change of dose, discontinuation of the drug, more frequent follow-up assessments, further diagnostic investigation, etc.

Hospitalization, Prolonged Hospitalization or Surgery

Any adverse event that results in hospitalization or prolonged hospitalization should be documented and reported as a serious adverse event unless specifically instructed otherwise in this protocol. Any condition responsible for surgery should be documented as an adverse event if the condition meets the criteria for an adverse event.

Neither the condition, hospitalization, prolonged hospitalization, nor surgery are reported as an adverse event in the following circumstances:

- Hospitalization or prolonged hospitalization for diagnostic or elective surgical procedures for a preexisting condition. Surgery should **not** be reported as an outcome of an adverse event if the purpose of the surgery was elective or diagnostic and the outcome was uneventful.
- Hospitalization or prolonged hospitalization required to allow efficacy measurement for the study.
- Hospitalization or prolonged hospitalization for therapy of the target disease of the study, unless it is a worsening or increase in frequency of hospital admissions as judged by the clinical investigator.

9.2.2 Adverse Event Causality

The Investigator will use the following definitions to assess the relationship of the adverse event to the use of study treatment:

Related - An adverse event has a strong temporal relationship to study drug, recurs on rechallenge or is known to be an effect of the study drug. Another reasonable etiology either doesn't exist or is unlikely.

CONFIDENTIAL

This material is the property of the study sponsor. Do not disclose or use except as authorized in writing by the study sponsor

Printed on 1/31/2017

Possibly Related - An adverse event has a strong temporal relationship to the study drug and an alternative etiology is either equally or less likely when compared to the potential relationship to study drug.

Not Related - An adverse event is due to an underlying or concurrent illness or effect of another drug and is not related to the study drug (e.g., has little or no temporal relationship to study drug or has a much more likely alternative etiology).

9.3 Reporting of Serious Adverse Events and Unanticipated Problems

Investigators are required to report to the Sponsor-Investigator ANY serious adverse event (SAE) as soon as possible. An SAE is any sign, symptom or medical condition that emerges during treatment or during a post-treatment follow-up period that (1) was not present at the start of treatment and it is not a chronic condition that is part of the patient's medical history, OR (2) was present at the start of treatment or as part of the patient's medical history but worsened in severity and/or frequency during therapy, AND that meets any of the following regulatory serious criteria:

- Results in death
- Is life-threatening
- Requires or prolongs inpatient hospitalization (planned hospitalizations are not considered an SAE)
- Is disabling or incapacitating
- Is a congenital anomaly/birth defect
- Is medically significant or requires medical or surgical intervention to prevent one of the outcomes listed above.

Serious adverse events require immediate notification to the following party below, beginning from the time of the first study treatment through and including 30 calendar days after the last treatment administration of ipilumimab. All emergent SAEs should be communicated to:

[name] MD PhD
[contact]
[contact]
[contact]
or via the UW Paging operator [name]

SAEs will be reported to the Cancer Consortium IRB in accordance with the AE reporting policy.

